7.6 Data source(s)

7.6.1 Context and rationale for data source(s)

The data source used in this study obtains clinical data from multiple partnerships across the U.S. These partnerships include data from organizations that aggregate data from oncology practices. The data vendor receives the complete EHR from each practice, including unstructured notes and scanned documents attached to the EHR. Structured and unstructured data are semi-normalized using an Observational Medical Outcomes Partnership (OMOP)-based common data model to improve uniformity across original data sources. Data curation (i.e., abstraction) of unstructured data from provider notes, pathology and imaging reports, and scanned documents is performed by trained reviewers. Natural Language Processing (NLP) is used to identify relevant strings of data within the patient record, but all curated data points are reviewed, interpreted, and documented by a human curation team. Patients are not filtered on the basis of data completeness to allow for flexibility when selecting the analytic sample.

Reason for selection: The dataset was considered due to its focus on oncology EHR data and was further considered fit-for-purpose after a detailed feasibility assessment that considered available sample size and completeness and quality of key inclusion criteria, exclusion criteria, key confounders, and outcomes. ([Appendix B](#)). Linked exposure and outcome data will not be accessed prior to conducting final analyses.

Strengths of data source(s): The dataset includes individuals from all regions of the U.S. and both community and academic providers. Due to the oncology focus of the data vendor, this dataset provides information on important diagnostic, prognostic, and clinical characteristics among breast cancer patients. The data include several important curated fields, including ECOG, line of therapy, and progression, using a broad range of clinical documentation (e.g., physician notes, pathology reports, etc.).

Limitations of data source(s): Algorithms used by the data vendor to derive treatment regimens and certain key variables such as those used to define key inclusion and exclusion criteria, potential confounders, and mortality have not been validated. The data are also limited by the accuracy of data collection in the original EHRs, the subjective nature of data abstraction, and, for some variables, the inability to determine whether missing values indicate the true absence of a condition or missing data.

Data source provenance/curation: The data vendor programmatically tracks all inbound data throughout the data pipeline for data provenance and quality control using internal identifiers. Additionally, the data curation process is operationalized to ensure consistency and high inter-rater reliability. To reduce data entry errors following abstraction, data curation software is utilized. Quality control analyses on various subsets (e.g., a random sample, a specific cohort, only curated patients) before data are finalized for external use.

Table 12. Metadata about data sources and software

Data Source(s):	[Redacted]
Study Period:	Start of all available data-July 20, 2023
Eligible Cohort Entry Period:	February 1, 2010-June 20, 2023
Data Version (or date of last update):	Q3 2023
Data sampling/extraction criteria:	Described above
Type(s) of data:	Clinical data sourced from oncology practices in the U.S.
Data linkage:	N/A
Conversion to Common Data Model:	Observational Medical Outcomes Partnership-based Common Data Model
Software for data management:	Aetion Substantiate Version 5.01 (or latest version)

N/A = not applicable

7.7 Data management

Raw data review

At Aetion, as part of the data ingestion process, raw data review is routinely conducted to understand contents of the data table(s), establish relationships, and help inform the database connection specification. Scientific integrity checks are performed to understand if the contents of the data shipment is consistent with the expected data as laid out in the applicable data usage agreement. Some of the key characteristics explored in this process include:

- Table structure (number of rows, columns, column names etc.)
- Summary counts per table (i.e., non-missing counts, unique counts)
- Variable distribution (e.g., min, mean, median, max for numeric variables; top frequencies for categorical variables)
- Date range (min, max and distribution over a time period)

- Missingness percentage of attributes

Database connection (DBC) process

Following receipt and review of the raw data, a data connector specification is drafted by a data scientist. The specification provides a map to Engineering for transformation of raw data to the Aetion longitudinal patient timeline. It includes information such as:

- Overall schema including tables (event types), rows (events), and columns (attributes); derivation of attributes to improve data flexibility on Platform and rationale for any attributes or events that are dropped
- Event dates that define how data will be reflected on the longitudinal patient timeline, and any minimal processing rules (e.g., drop an event that does not include a start or end date)
- Skeleton structure diagram that represents the logical view of the entire database, defining how the data tables are organized and related in the longitudinal patient timeline and how the relations among them are associated
- Information for user interface and labeling
- Codes and definitions; typically used to substitute users' having to look-up multiple resources to understand/process data

Validation of the DBC is completed to ensure that the implementation of DBC logic leads to transformed data output that connects to and behaves within Aetion Substantiate exactly as intended. Raw data are never loaded as-is; rather, data are transformed (via the DBC) into a longitudinal sequence of healthcare data points for each patient. DBC validation is required to confirm that this transformation was performed correctly. This helps to ensure validity/accuracy of the connected data and its importance cannot be ignored. Validation is performed via double programming, where two different people work independently from the same DBC specification and then compare their output. The DBC is considered validated if the outputs are identical. If the outputs are not identical, then the source of the discrepancy is investigated and resolved.

Following validation, the specification files are used to create an Aetion data dictionary for the dataset. In addition, throughout the data connector spec / creation process, any issues or decisions that have to be made that are not otherwise specified in the Specification files (e.g., how missing dates are handled), are noted in the data dictionary.

7.8 Quality control

Prior to deployment on Aetion Substantiate, a manual test of certain platform features and dataset values is conducted to ensure they are visible and testable on the front-end. This test is run following any deployment activity (such as a version update and/or data/shard update). Checks include:

- Baseline values for database information (dataset name, patient counts, earliest and latest event dates)
- Database configuration (specified dataset values)

- Measure, Cohort, and Analysis Generations to confirm this functionality using the dataset
- Output from generated analysis output
- Coding Systems, if applicable

The implementation of all variables, cohorts, and analytic plans will be individually checked by two analysts. Any discrepancies will be discussed with the analysts and study lead to ensure alignment with the study design outlined in the protocol.

7.9 Study size and feasibility

The PALOMA-2 trial target sample size was 650 patients with 1:1 randomization. This sample size was based on 90% power to detect a hazard ratio for progression of 0.69 at a one-sided alpha level of 0.025 (assuming 347 events).² A total of 666 patients were included in the trial.

Sample size requirements to detect a range of hazard ratios relevant to the PALOMA-2 trial are presented in [Table 13](#). If the unweighted study sample size falls below the lowest estimate, corresponding to the required sample size to detect the point estimate for the hazards of progression or death observed in the trial with 80% power, implementation will pause. The study team and CARE Steering Committee will then consider the value of continuing the study with potentially insufficient power, given the lower primacy of statistical significance in an emulation setting.

Table 13. Sample size requirements

	Power	Hazard ratio for death	Ratio of exposed to unexposed	Alpha	Prevalence of death among the unexposed ^a	Total sample size required ^b
Trial sample size calculation, point estimate	90%	0.69	1:1	5%	57.7%	530
Trial sample size calculation, point estimate	80%	0.69	1:1	5%	57.7%	396
Trial result, upper confidence limit	90%	0.72	1:1	5%	57.7%	675
Trial result, upper confidence limit	80%	0.72	1:1	5%	57.7%	505
Trial result, point estimate	90%	0.58	1:1	5%	57.7%	246
Trial result, point estimate	80%	0.58	1:1	5%	57.7%	184

^a As reported in the trial.

^b Calculated using the *powerSurvEpi* R package²⁴, based on the sample size formula for proportional hazards modeling derived by Latouche et al.²⁵

In feasibility analyses ([Appendix B](#)) among adult, postmenopausal females with metastatic breast cancer and no evidence of ECOG performance status ≥ 2 in the data source, there were 944 individuals with evidence of initiating both palbociclib and letrozole, and 660 individuals who initiated letrozole only. This real-world study will include data for all individuals meeting study inclusion and exclusion criteria.

8. Strengths and Limitations

This emulation study is limited by several inherent differences between trial settings and non-interventional studies leveraging RWD.

In the absence of randomization, IPTW will be used to control for confounding. However, important confounders may be unavailable or imperfectly measured in the RWD source, which may result in residual confounding. There may be residual confounding by indication arising from causes of progression that also impact physicians' treatment decisions. Several measures of disease severity (e.g., performance status, stage at initial diagnosis, disease-free interval) will be used to generate treatment probabilities, but these may not sufficiently control for confounding by indication. In particular, real-world patients who did not initiate palbociclib after approval may systematically differ from those treated with palbociclib for reasons that are not captured in the health record. These patients may also be different from those enrolled in the PALOMA-2 RCT, limiting successful emulation of the trial results.

Several trial design elements cannot be perfectly emulated or operationalized due to limitations of the data source. First, the trial included international sites, while the RWD source is restricted to EHR data from U.S. oncology clinics. Second, while patients with locoregionally recurrent disease were included in the trial, similar patients cannot be identified in the data source. These patients constituted a small proportion of the original trial population ($<3\%$ in each arm), but restriction of the real-world population to patients with metastatic disease does limit the comparability of the two populations. Third, some study inclusion and exclusion criteria and potential effect modifiers, such as measurable disease, cannot be operationalized and others, such as performance status, lab values, and patient symptoms, may be missing in the RWD due to infrequent real-world clinical assessment or inadequate capture in the EHR. Excluding patients who have missing values for these key variables may result in systematic differences between the trial and real-world populations. A preliminary data feasibility assessment was conducted prior to protocol finalization to ensure that key study eligibility criteria and potential confounders had a high degree of completeness ([Appendix B](#)). Fourth, while trial treatments were administered on the same day, these treatment strategies must be approximated (within 15 days) due to differences in medication dosing schedules, insurance delays, and provider decision-making in routine clinical practice. Finally, progression surveillance is conducted less frequently and regularly in real-world practice than was performed in the trial, which may affect estimates of rwPFS.

At the same time, this study proposes to use a high-quality, RWD source specifically designed for conducting RWD analyses in oncology. The data source includes curated, quality-controlled data elements (e.g., ECOG, progression) unique to oncology studies and necessary to this emulation. The preliminary feasibility assessment indicated low missingness of key variables, the ability to create a trial similar population through careful operationalization of trial characteristics, and a larger available sample size than was enrolled in the trial. Differences between

the trial and real-world emulation, including rates of study treatment discontinuation and crossover, will be transparently reported and compared to contextualize final results.

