7.4 Variables

7.4.1 Context and rationale for exposures of interest

Operational definitions for the two treatment strategies that will be compared are presented in [Table 6](#). Exposure will be defined based on treatment initiated during the 15-day exposure ascertainment window. While patients in the PALOMA-2 trial received study treatments on the same day, a 15-day window was selected to allow for potential delays in data entry and treatment administration variability that may occur in routine practice. In a feasibility assessment of 944 patients in the data source who initiated both letrozole and palbociclib as first-line therapy, 93.3% started both medications within 15 days. A shorter exposure window may be too restrictive and result in few eligible patients, while longer time periods may result in treatment patterns in the study population that are vastly different from the trial. As discussed above, patients who experience a censoring event or death during the exposure ascertainment window will be excluded from the study to align the start of follow-up for both exposure groups.

Table 6. Operational Definitions of Exposures

Group name(s)	Details	Washout window	Assessment Window	Incident with respect to...	Source of algorithm	Validity concerns and how they will be addressed
Exposed	Patients initiating treatment with palbociclib and letrozole within 15 days of one another, in the metastatic setting	N/A, treatment in first-line metastatic setting	[Metastatic diagnosis date, Day -1]	Metastatic Diagnosis	Curated regimen definition; clinical experts	Real-world exposure group definitions allow for more flexibility in treatment timing than in the trial. The potential impact of this on results will be explored through a sensitivity analysis shortening the duration of the exposure ascertainment window (Table 11).
Comparator	Patients initiating treatment with letrozole with no evidence of palbociclib treatment within 15 days, in the metastatic setting	N/A, treatment in first-line metastatic setting	[Metastatic diagnosis date, Day -1]	Metastatic Diagnosis	Curated regimen definition; clinical experts	

N/A = not applicable

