Appendix B: Preliminary feasibility assessment

STEP 1: STATE RESEARCH AIM, QUESTION, AND OBJECTIVES					
STEP 1a: Overarching research aim					
To emulate the PALOMA-2 randomized controlled trial of letrozole + palbociclib as first-line treatment in postmenopausal women with estrogen receptor-positive/human epidermal growth factor receptor 2-negative advanced breast cancer using real-world data.					
STEP 1b: Trial research question					
Among adult postmenopausal women with estrogen receptor-positive/human epidermal growth factor receptor 2-negative advanced breast cancer, does initial treatment with letrozole + palbociclib compared with treatment with letrozole alone result in longer progression-free survival?					
STEP 1c: Trial primary objective(s)					
Among adult postmenopausal women with estrogen receptor-positive/human epidermal growth factor receptor 2-negative advanced breast cancer, compare progression-free survival for patients treated with palbociclib and letrozole and patients treated with letrozole alone.					
DESIGN ELEMENTS	STEP 2: DESCRIBE ORIGINAL CLINICAL TRIAL	STEP 3: DESCRIBE REAL-WORLD DATA STUDY EMULATION OF ORIGINAL CLINICAL TRIAL		Data Source	
		3a. Minimal criteria for valid operationalization in real-world data source	3b. Criteria ranking with regard to uniqueness and importance		
OVERALL RATING				5	
GENERAL					
Sample size	Trial sample size	1.5x trial sample size ²	Must Have	Sample size among adult patients with metastatic breast cancer treated with first-line letrozole or letrozole + palbociclib ³	
Treated	444	666		1,148	5
Comparator	222	333		1,086	5
Length and frequency of follow-up ¹	Median reported follow-up: 23 months (range not reported)	Sufficient time coverage in dataset to identify outcome after receipt of treatment	Must Have	Earliest metastatic diagnosis date: Q3 1980 End of data cut: Q3 2023	Not Applicable⁴
VARIABLE-RELATED					

Variable	Trial criterion	Minimal criteria for valid operationalization in any real-world data source based on routine clinical care	Criteria ranking with regard to uniqueness and importance	Operationalization and coverage in data source	Rating
Treatment	125 mg of palbociclib per day, administered orally in 4-week cycles (3 weeks of treatment followed by 1 week off); 2.5 mg of letrozole per day, administered orally (continuous treatment)	Date of palbociclib and letrozole treatment	Must Have	Date of palbociclib and letrozole treatment is available. Lines of therapy are available.	5

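### Section 7.9 describes PALOMA-2 as 1:1 although Appendix B shows 444 versus 222, and Table 13 with its 184-patient pause threshold assumes a 1:1 split that the section's own cohort count does not have

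*Combined protocol and SAP*

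**What the plan says.** On the trial, section 7.9 states: "The PALOMA-2 trial target sample size was 650 patients with 1:1 randomization". It says this size was based on "90% power to detect a hazard ratio for progression of 0.69 at a one-sided alpha level of 0.025 (assuming 347 events"), and that "A total of 666 patients were included in the trial".

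The sample-size rows of Appendix B give, for each arm, the trial's own size followed by a feasibility minimum of "1.5x trial sample size": "Treated 444 666" and "Comparator 222 333". The trial figures are therefore 444 and 222.

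On this study, Table 13 in section 7.9 lists six required totals (530, 396, 675, 505, 246, 184). Every row has a 1:1 ratio of exposed to unexposed, 5% alpha and a 57.7% event proportion. The lowest, 184 (HR 0.58, 80% power), is a decision rule: if the unweighted sample falls below it, implementation pauses and the study team and Steering Committee consider whether to continue. The section then reports feasibility counts: "there were 944 individuals with evidence of initiating both palbociclib and letrozole, and 660 individuals who initiated letrozole only". Section 7.4.1 adds that, of the 944 who initiated both drugs, "93.3% started both medications within 15 days".

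**The concern.** The trial is the benchmark for the whole emulation, and its randomization ratio is described in two incompatible ways. The 1:1 ratio is then used in every row of the sample-size table, two of which are labelled as the trial's sample size calculation, and in the threshold that governs whether the study proceeds.

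For a given total and event proportion, an unequal split carries less information about the hazard ratio than an equal one. A threshold computed at 1:1 and expressed only as a total therefore overstates the power of any unbalanced cohort that just clears it. The eligible cohort's split is unknown until all criteria in Tables 4 and 5 have been applied.

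**Working it through.** **1. The trial's ratio.** From Appendix B, 444 + 222 = 666, the number 7.9 says were included, and 444/222 = 2.0. The split is exactly 2:1.

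**2. Do the trial's design figures fit?** Inputs from 7.9: HR 0.69, one-sided 0.025, 90% power, 347 events. Schoenfeld's formula, with p the share in the treated arm, is

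events = (1.960 + 1.282)² / [p(1−p) · (ln 0.69)²], where (1.960 + 1.282)² = 10.507 and (ln 0.69)² = 0.1377.

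- 1:1, p(1−p) = 0.25: 305.3, so 306 events.
- 2:1, p(1−p) = 0.2222: 343.4, so 344 events.

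The stated 347 is close to the 2:1 result. With 347 events, power would be 93.3% at 1:1 and 90.3% at 2:1. Freedman's formula gives 313 at 1:1 and 310 at 2:1, so it reaches 347 at neither ratio.

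**3. Reproducing Table 13.** Total = (z for two-sided 5% + z for power)² / [p(1−p) · (ln HR)² · 0.577], at p = 0.5. All six totals reproduce exactly. For the lowest row, 7.849 / (0.25 × 0.2967) = 105.8 events, and 105.8 / 0.577 = 183.4, so 184.

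**4. Cohort counts under the 15-day rule.** 0.933 × 944 = 881, so about 63 of the 944 fall outside the exposed definition. The documents do not say how many of the 63 would become comparators. As an assumption I take the two extremes: all dropped (881:660), or all moved to the comparator group (881:723, since 660 + 63 = 723).

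**5. The pause threshold and the power of 184 patients at other splits** (HR 0.58, two-sided 5%, 57.7% events):

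| Exposed : comparator | Source | Total for 80% power | Power with 184 patients |
|---|---|---|---|
| 1:1 | Table 13 | 184 | 80% |
| 1,148:1,086 | Appendix B, broader count | 184 | 80% |
| 881:723 | 7.9 with the 15-day rule, 63 moved | 186 | 80% |
| 881:660 | 7.9 with the 15-day rule, 63 dropped | 188 | 79% |
| 944:660 | 7.9 as printed | 190 | 79% |
| 2:1 | illustration | 207 | 75% |

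At 2:1 every total rises by 12.5% (0.25/0.2222 = 1.125). At 944:660 the six totals would be 547, 408, 697, 521, 254 and 190.

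**6. Distance from the threshold.** 944 + 660 = 1,604 feasible patients, 8.7 times 184. At that size and split, with 57.7% events, power exceeds 99.8% at HR 0.58, 0.69 and 0.72.

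**The case against.** The strongest reply is that nothing decided in this study depends on the error. Feasible numbers exceed the threshold more than eightfold, crossing it leads only to a pause and a discussion, and section 5 says that agreement with the trial is not anchored to statistical significance. Appendix B also sets minimums per arm (666 and 333), and its counts meet both, so the split was not wholly ignored. All of this stands and limits the size of the point. The Appendix B minimums, however, are feasibility checks before attrition and are not part of the pause rule.

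Three stronger readings are tempting, and the documents do not support them.

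- A reader might infer that 347 events prove 2:1. They match 2:1 under plain Schoenfeld only. The documents give neither the trial's formula nor any allowance for interim analyses, and about 14% inflation at 1:1 (347/305.3) would also reach 347. The 444/222 split settles the ratio; the event count is supporting evidence.
- A reader might infer that Table 13 is miscalculated, or that its first two rows are a failed attempt at the trial's calculation. The arithmetic is right for its inputs. The table is introduced as covering a range of hazard ratios relevant to the trial, and the second row uses 80% power, so the labels are best read as the source of each hazard ratio. Changing the first row to 2:1 would give 596, not 650, because 57.7% differs from 347/650 = 53.4%.
- A reader might infer that the study is materially underpowered. No count in the documents suggests a 2:1 or more extreme cohort, and the broader Appendix B count is near 1:1.

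**Conclusion.** The point holds in a limited form. The statement that the trial was randomized 1:1 is contradicted by Appendix B and needs correction. The 1:1 input to Table 13 is not justified anywhere and does not match the 944:660 count in the same section. On the documents' own cohort counts the threshold of 184 would lie between 184 and 190: 186 to 188 once the 15-day rule is applied, and 190 on the count as printed. The 207 total and the 75% power at 2:1 are illustrations of why a threshold on the total alone is fragile; they are not forecasts for this cohort.

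These figures rest on the Schoenfeld-type formula that reproduces Table 13 and on 57.7% as the overall event proportion. Table 13 labels 57.7% as the proportion among the unexposed. If it applies to that group alone and hazards are proportional, the lowest row would be 219 at 1:1 and 234 at 944:660, a larger shift than the cohort's allocation causes. The go/pause decision is unlikely to change either way, and no estimand, model or effect estimate is affected.

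**What to change.** 1. In 7.9, correct the trial description to 2:1, consistent with 444 and 222 in Appendix B.
2. State in Table 13 that the row labels give the source of the hazard ratio and are not the trial's own sample-size calculation.
3. Recompute Table 13 and the pause threshold at the exposed-to-comparator ratio found once all eligibility criteria have been applied. Express the threshold as required events, or as a total with the split taken into account. When recomputing, say whether 57.7% is an overall or a comparator-only event proportion.
4. Beside the feasibility count, note that about 881 of the 944 meet the 15-day exposed definition.

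The cost is one corrected sentence, two clarifying notes and a recalculated table. No new data are needed and the analysis does not change. The requirement may become slightly less favourable.

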7.5 Data analysis

7.5.1 Context and rationale for analysis plan

Analytic Population

Primary analyses will be conducted in the real-world study population based on the first study treatment initiated. This approach is intended to emulate the intent-to-treat analysis conducted in the PALOMA-2 trial, where patients were analyzed based on their randomized treatment assignment. As crossover between treatment arms was not allowed in the PALOMA-2 trial, intent-to-treat and per-protocol trial analyses would produce equivalent results. Conversely, real-world patients initially prescribed letrozole could initiate palbociclib after the end of the exposure ascertainment window. To investigate the potential for crossover between comparison groups prior to disease progression in the real-world population, descriptive analyses of all first-line treatments initiated and time between treatments will be conducted.

IPTW will be used to approximate full conditional exchangeability between the comparison groups and facilitate estimation of the population average treatment effect.¹⁶⁻¹⁸ Propensity scores (PS) reflecting the conditional probability of initiating treatment with palbociclib and letrozole will be calculated via multivariable logistic regression. Exposure to palbociclib and letrozole will be regressed on *a priori* identified potential confounders ([Table 9](#)). Inverse probability of treatment weights will be calculated as the inverse of the propensity score (1/PS) for patients in the exposed group and as the inverse of one minus the propensity score (1/1-PS) for comparator patients.¹⁹ Patients are therefore weighted by the inverse probability of initiating the treatment they actually started, conditional on the observed covariates included as independent variables in the PS model. This approach aims to create a pseudo-population with full exchangeability on measured confounders within which the treatment effect is estimated.

Confounder balance will be assessed by comparing the absolute standardized difference (ASD) in the distribution of categorical variable levels and the mean of continuous variables between the weighted exposure groups.¹⁶ If balance is not achieved (ASD > 0.1), alternative specifications of the PS model, e.g., including variable transformations and interaction terms, will be explored. Confounders with insufficient balance may also be included as covariates in the outcome models.

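### The pause rule compares an unweighted patient count with a Table 13 total that makes no allowance for weighting, so 184 patients give 80% power only if the weights cost nothing

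*Combined protocol and SAP*

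**What the plan says.** Section 7.9 lists total sample sizes for three hazard ratios at 80% and 90% power (Table 13). The lowest row reads "Trial result, point estimate 80% 0.58 1:1 5% 57.7% 184". The footnote says the totals are "based on the sample size formula for proportional hazards modeling" and names the package used. The listed inputs are power, hazard ratio, allocation ratio, alpha and event proportion. None of them relates to weighting or confounding.

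The pause rule is tied to that lowest row. It applies "If the unweighted study sample size falls below the lowest estimate, corresponding to the required sample size to detect the point estimate"; the row meant is the one for HR 0.58 at 80% power. When the rule is triggered, the study team and steering committee decide whether continuing is worthwhile.

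The primary analysis is weighted. Section 7.5.1 states that "IPTW will be used to approximate full conditional exchangeability between the comparison groups and facilitate estimation of the population average treatment effect". The weights are unstabilised (1/PS and 1/(1-PS)), and Table 10 fits the Cox model in the weighted population. Table 10 leaves truncation or stabilisation as an option if extreme weights appear. The plan nowhere states a design effect, inflates Table 13 for weighting or mentions an effective sample size.

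**The concern.** The threshold and the analysis do not match. The total of 184 is the requirement for a comparison in which every patient counts equally. Under inverse probability weighting, a few patients with large weights can dominate, and the variance of the log hazard ratio then behaves as if the sample were smaller. Counting unweighted patients against an uninflated total ignores this loss.

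The loss could be material here. Year of treatment initiation is a candidate propensity score covariate (Table 9). Entry starts in February 2010 (Section 7.3.1), while Table 11 places accelerated approval of palbociclib in February 2015. Calendar year should therefore predict treatment strongly, which is the situation that produces variable weights.

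At stake is whether the steering committee's pause rule measures what it says it measures. A cohort slightly above 184 would pass as having 80% power when its weighted analysis may have clearly less.

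**Working it through.** **Inputs.** From Table 13: HR 0.58, 0.69 and 0.72; power 80% and 90%; 1:1 allocation; alpha 5%; event proportion 57.7%. The table does not give the sidedness of alpha. Two-sided 5% reproduces its totals and corresponds to the trial's own one-sided 0.025; one-sided 5% would give about 145 for the lowest row instead of 184. The 57.7% is used as the overall event proportion, because that is how the table reproduces.

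**Step 1: reproduce Table 13.** Events = (1.96 + z)² / (0.25 × (ln HR)²), and N = events / 0.577.

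For HR 0.58 at 80% power: (1.96 + 0.842)² / (0.25 × 0.2967) = 105.8 events, and 105.8 / 0.577 = 183.4, rounded up to 184.

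| HR | Power | N before rounding | Table 13 |
|---|---|---|---|
| 0.69 | 90% | 529.03 | 530 |
| 0.69 | 80% | 395.18 | 396 |
| 0.72 | 90% | 674.99 | 675 |
| 0.72 | 80% | 504.21 | 505 |
| 0.58 | 90% | 245.48 | 246 |
| 0.58 | 80% | 183.37 | 184 |

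All six agree with no inflation term. With 184 patients and no weighting, expected events are 184 × 0.577 = 106.2 and power is 80.1%.

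**Step 2: allow for weighting.** If weighting leaves a fraction f of the effective sample, take the events as 106.2 × f. Then power = Φ(0.5 × |ln 0.58| × √(106.2 f) − 1.96), and the N for 80% power is 183.37 / f. The documents do not give f, so these values are assumed.

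| Loss of effective sample | f | Power at 184 | N for 80% power |
|---|---|---|---|
| 0% | 1.0 | 80% | 184 |
| 10% | 0.9 | 76% | 204 |
| 20% | 0.8 | 71% | 230 |
| 30% | 0.7 | 65% | 262 |
| 50% | 0.5 | 51% | 367 |

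**Step 3: simulation check.** This used 184 patients, HR 0.58, ten covariates that predict treatment but not outcome, an estimated propensity score, robust variance and 1,500 replicates per scenario. Power was 79% unweighted. With weighting it was 73%, 65% and 56% when the mean effective fraction was 86%, 68% and 51%. The direction and approximate size agree with Step 2. The strength of treatment prediction was assumed.

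**Step 4: compare with the feasibility counts.** 944 + 660 = 1,604 patients. If all remained, 80% power at HR 0.58 would survive a design effect of 1,604 / 183.37 = 8.7. At f = 0.5 the effective total is 802, above every row of Table 13. At f = 0.4 it is 1,604 × 0.4 = 642, above every row except 675.

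**The case against.** The strongest reply is that the gap is unlikely to matter. The final cohort would have to fall from 1,604 to about 184, a loss of 1 − 184/1,604 = 89%, before the threshold came into play, and nothing in the documents suggests attrition on that scale. The rule only leads to a pause and a discussion. Section 5 chooses a measure of agreement that does not rest on statistical significance, and Section 7.9 repeats that significance is secondary. Appendix B also has its own minimum of 666 treated and 333 comparator patients, set to absorb attrition, and the data source met it with 1,148 and 1,086. All of this stands, and it limits the practical impact. It does not repair the threshold. The Appendix B minimum is a screen before full eligibility and does not address weighting. The 1,604 are described by age, sex, menopausal status, metastatic disease and performance status only, so the remaining exclusions are still to come.

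A second reply is that the loss may be smaller than shown. Truncation can recover some precision: capping weights at the 95th percentile gave power of 0.70 to 0.75 in simulations with non-prognostic covariates, but it did not help when covariates were prognostic. Adding baseline covariates to the Cox model, as the equation in Table 10 prints it, also raised power, though partly through a type I error of 7% to 12%. The plan relies on neither and quantifies neither. So the direction stands and the size remains an assumption.

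Two stronger readings are tempting. A reader might infer that this study will be underpowered, or that the rows for HR 0.69 and 0.72 will not be met. Step 4 does not support this unless an attrition assumption is added, and the documents give none. A reader might also infer that Table 13 is miscalculated. It is not.

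**Conclusion.** The point holds in a limited form. Table 13 is correct for an unweighted 1:1 comparison, but the pause rule attaches its 80% power to an unweighted count that feeds a weighted analysis. Once the weights vary, the stated power at 184 is too high: 76% to 51% for assumed losses of 10% to 50%, with 204 to 367 patients needed in place of 184.

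These figures rest on an assumed loss, on treating 57.7% as the overall event proportion, and on the approximation that information falls in proportion to the effective sample size. The mismatch becomes consequential if attrition is severe or the weights are highly variable. The second is plausible given the role of calendar year; the first cannot be judged from the documents. The change should be made because it corrects a stated power and a decision threshold at little cost. It is not evidence that the study as expected will fail.

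**What to change.** 1. Label the Table 13 totals as required effective sample sizes, and add the unweighted N for assumed effective fractions of 0.4 to 0.8. For the 184 row this is about 459 (183.37 / 0.4) down to 230 (183.37 / 0.8); for the 675 row, about 1,688 down to 844.
2. Apply the pause rule to the Kish effective sample size, (Σw)² / Σw². Compute it within each arm and sum over the two arms before comparing it with the Table 13 total, or compare each arm with half the total. A single arm's value must not be set against the full total, because that would double the threshold.
3. Use the final weights, after any truncation or stabilisation. The weights need only exposure and baseline data, so the check can be made before outcomes are linked and respects the commitment that "Linked exposure and outcome data will not be accessed prior to conducting final analyses".

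The cost is a few sentences, an extended table and one outcome-blind calculation. The downside is that the stated requirement looks less favourable. The Kish figure is also only an approximation to the loss of precision in the hazard ratio, and the text should say so.
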